2.4 Determination of sample size

The outcome(s) on which the sample size calculation is based upon, is the primary endpoint measurement of oxygenation, defined as ratio of PaO₂/FiO₂.

The target difference is the difference from baseline measured at the primary endpoint (at day 6 and day 15) between the control and the treated group. Given a sample size of 81 participants, 54 on Zilucoplan® and standard of care and 27 on standard of care there would be >85% power to show a significant difference from standard of care at the 2 sided 5% level if the true underlying treatment difference was an 80 point difference (25% of 320, being the mean at hospital admission) in the PaO₂/FiO₂ ratio. This assumes a standard deviation of 105 and a dropout rate of less than 10%.

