
patient remained in hospital, the patient will be classified as a responder, even though the 2-point change had not been ‘sustained’.
	
date). If Time to Response >15 and censor=1 for analysis up to D15, Time to Response=15. If Time to Response >28 and censor=1 for analysis up to D28, Time to Response=28. For patients who have died Time to Response is set to D15 or D28 respectively and censored at this time. Note: Treatment will be merged into the TTE dataset. In addition to other variables that may be used as covariates in final analysis.
 
(one line per participant dataset)
	

Objective 2 Percentage of participants reporting at least a 2-point improvement sustained to D28 or discharge
	
Use D28 response indicator variable defined above
	
PROC FREQ/PROC LOGISTIC(if covariates are added) Model: Response=ACTARM +covariates (if added) Output percentage response on each treatment. Odds ratio and 95% confidence interval

Objective 2 AUEC/Time using the 6-point score recorded daily – up to D15, D28 and all data recorded
	
For each participant calculate the area under the curve and divide by 15 for up to D15 and by 28 for up to D28 (higher average score per day the better the response). Use last value brought forward for any missing values until next data entry. For discharge, carry forward score=6 for each day post discharge day. For death, carry forward score=1 for each day post death day.
	
Analyse AUEC/Time using analysis of variance with ACTARM as a two-level factor and baseline score as a covariate

Endpoint	Derivation	Analysis

Objective 2 Percentage of participants who record at least 2-point improvement from baseline or discharge (response) between D1-D6, D7-D15 and D16-D28
	
Responder classified as above. Create indicator variable (3 levels) if the relative day of START of response is between D1 and D6, between D7 and D15 or between D16 and D28. Each responder participant can only be within one of these categories. Participants who have a missing value are classified as non-responders
	
Frequency table and percentage responders in each of the categories defined by the indicator variable, by treatment. Exact 95% confidence intervals for each percentage

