
Objective 2
 
Time since randomization until absence of LAST fever (defined as 37.1°C or more) for more than 48 h without antipyretics (use last fever to account for possibility that participants have intermittent fever per this definition)
	
Antipyretic use in last 24 hours is collected on eCRF on every day. Use highest temperature recorded in last 24 hours, not the 7-10am temperature to identify the date when the last fever ended per definition.
 
Create variable which contains number of days between this date and date of randomisation for each participant. If a participant has had no episodes of the fever, the number of days is 0.
 
Create indicator variable (censor) to indicate if participant has recovered from the last fever at time of analysis (0=recovered, 1=fever is ongoing at time of analysis). If a participant has had no fever, (i.e. time=0), censor=0.
	
Kaplan-Meier analysis using PROC LIFETEST. Strata ACTARM.
 
Request Failure plot adjusting axis and heading titles to reflect responder and not failure
 
Output statistics:
 
Appropriate statistics from analysis as indicated in mock shell

Endpoint	Derivation	Analysis

Objective 2
 
Duration of hospital stay
 
Duration of hospital stay of survivors
	
Calculate duration of hospital stay in days (Hospital Discharge date-Hospital Admission date)
 
Create indicator variable to flag survivors
	
Summary statistics: n, nmissing, mean, SD, median, minimum, maximum
 
By treatment arm

Objective 2
 
Number of days requiring supplemental oxygenation after randomisation to Day 28 (or discharge, whichever comes earlier)
	
Number of days where Suppl O₂ = ‘Y’ from Vital parameters
	
Summary statistics: n, nmissing, mean, SD, median, minimum, maximum
 
By treatment arm

Objective 2
 
Time since randomization until improvement in oxygenation (defined as independence from supplemental oxygen) during 28 day assessment period (or discharge, whichever comes earlier)
	
Independence from supplementary oxygen means no further ‘Y’ after a ‘N’
	
Kaplan-Meier analysis using PROC LIFETEST. Strata ACTARM.
 
Request Failure plot adjusting axis and heading titles to reflect responder and not failure
 
Output statistics:
 
Appropriate statistics from analysis as indicated in mock shell

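### Two Kaplan-Meier recovery endpoints in SAP Table 8.1 (off oxygen, end of last fever) have no rule for deaths; under the usual default the 28-day recovery percentage would be overstated

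*SAP*

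**What the plan says.** SAP section 8.2, Table 8.1, contains three time-to-recovery rows under Objective 2. All three use PROC LIFETEST by actual arm and display a failure curve with the labels changed to read as response.

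- **Oxygen row:** "Time since randomization until improvement in oxygenation (defined as independence from supplemental oxygen) during 28 day assessment period (or discharge, whichever comes earlier"). The derivation column defines the event only: no later day on oxygen after a day off it. It assigns no time or censor value to anyone without the event.
- **Fever row:** the time runs from randomisation to the date the last fever ended. On censoring it says "Create indicator variable (censor) to indicate if participant has recovered from the last fever at time of analysis", with two codes, recovered or still ongoing. A participant who never had fever is given time 0 and counted as an event. Death is not mentioned.
- **2-point response row:** "For patients who have died Time to Response is set to D15 or D28 respectively and censored at this time".

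Other parts of the SAP bear on the gap without closing it. Section 4.2 names death as a form of missing data, describes such patients as no longer at risk of recovery, and leaves the handling to each endpoint's own section. Section 3.2.1.3 says that patients who die in hospital do not count as discharged, so the discharge limit in the oxygen row does not cover them. Section 3.1 plans confidence limits but no p-values for secondary endpoints. Current protocol section 4.3 lists both endpoints as exploratory.

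**The concern.** Kaplan-Meier treats a censored patient as someone who could still have the event later at the same rate as those still under observation. A patient who has died on oxygen or with fever cannot recover. If such patients leave the risk set at death, one minus Kaplan-Meier estimates recovery in a hypothetical setting without death, and it exceeds the proportion who actually recover.

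The excess grows with mortality, so it is larger in whichever arm has more deaths, and that would shrink a real difference in recovery between arms. For an analysis meant purely for estimation, the reported 28-day percentage would not mean what its relabelled axis says.

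The fever row has a second problem. A patient who dies with fever ongoing has no date on which the last fever ended, and so may have no time value at all. A patient who never had fever and then dies is counted as recovered on day 0.

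**Working it through.** **The plan's own figures.** The documents give no figure for either endpoint. The only calculation is the power for PaO2/FiO2 (SAP 2.4): "Given a sample size of 81 participants, 54 on Zilucoplan® and standard of care and 27 on standard of care", difference 80, SD 105, two-sided 5%. It reproduces: 80 / (105 × √(1/27 + 1/54)) = 3.23, and 3.23 − 1.96 = 1.27, giving 89.8%. With 10% dropout (24.3 and 48.6 patients) it gives 86.6%, against a stated value above 85%. It has no bearing on this point.

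**Inputs.** R is the true proportion recovered by day 28 and D the proportion who died first.
- D: protocol 2.2 gives about 5% of infected patients ventilated, 40-50% of those dying, and 15-20% of infected patients admitted. Deaths per admission are then 5% × 40% / 20% = 10% to 5% × 50% / 15% = 16.7%. These are general COVID-19 figures, not figures for the eligible population, so 5% is shown as well.
- R: 65-75%. This is an assumption; the documents give nothing.

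**Deaths censored when they occur.** With constant cause-specific hazards and no other censoring before day 28,

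1 − KM(28) = 1 − (1 − R − D)^(R/(R + D)).

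Example, R = 0.75 and D = 0.10: 1 − 0.15^(0.75/0.85) = 81.2%.

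| R | D | 1 − KM | Excess (points) |
|---|---|---|---|
| 65% | 5% | 67.3% | 2.3 |
| 75% | 5% | 77.9% | 2.9 |
| 65% | 10% | 69.9% | 4.9 |
| 75% | 10% | 81.2% | 6.2 |
| 65% | 17% | 74.3% | 9.3 |
| 75% | 17% | 87.2% | 12.2 |

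The binomial standard error √(R(1 − R)/n) is 5.9-6.5 points for n = 54 and 8.3-9.2 points for n = 27. At 10-17% deaths the excess is therefore between about half a standard error (4.9/9.2) and two (12.2/5.9).

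**Sensitivity to timing.** With early-peaking times instead (gamma, shape 2, scale 4.5 days for recovery and 6 days for death), simulation gives an excess of about 4-5 points at 10% deaths and 8-10 at 17%. If every death precedes every recovery, the curve reads R/(1 − D). If every death follows the last recovery, the excess is zero.

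**Febrile deaths dropped for lack of an end date.** This also gives R/(1 − D). At R = 75%: 0.75/0.90 = 83.3% (excess 8.3 points) at 10% deaths, and 0.75/0.83 = 90.4% (excess 15.4) at 17%.

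**Deaths held to day 28.** With no other censoring before day 28, nobody leaves the risk set early except by recovering, so 1 − KM(28) equals the observed proportion recovered. Simulation with n = 54 gave 85.0%, 80.1% and 70.1% for true values of 85%, 80% and 70% (mortality 5%, 10% and 20%). The same cases with censoring at death gave 88.6%, 87.1% and 83.3%.

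**Different mortality by arm (illustration).** Take 80% recovered and 10% dead in one arm, 70% and 20% in the other. The true 10-point difference in recovery reads as 87.1% − 83.3% = 3.8 points if deaths are censored when they occur.

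**The case against.** The strongest reply is that the SAP nowhere says deaths are censored when they occur. Other rows of Table 8.1 point towards day 28: the response row holds deaths there, and the row on first use of ventilation censors non-users at day 28. The ARDS row runs patients without progression to discharge or day 28. If the programmer follows that pattern, the bias is zero. Section 8.2 also refers to mock shells, which are not among the documents. This stands: the plan has an unspecified rule, and a reader who infers that the reported percentage is necessarily too high goes further than the text. It does not remove the point. Censoring at death is what ordinary use of the method does, the wording of section 4.2 leans that way, and that section defers to rows that are silent.

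Three more limits are fair:

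- It is tempting to say that the response row does not censor deaths and these two rows do. The response row censors them too; what differs is the censoring time.
- Not every death in the fever row is affected. A patient whose last fever had ended before death is an event. Counting a never-febrile death as recovered on day 0 may be intended if the endpoint is fever resolution as such, so this needs a statement and not necessarily a recode.
- A reader might infer that a mortality difference would be concealed. It would not be: 28-day mortality has its own odds ratio and interval, and the ordinal-scale table keeps deaths in its denominators.

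**Conclusion.** The point holds as a conditional one. Two recovery endpoints analysed by Kaplan-Meier lack a death rule that the same table supplies for a third. If deaths without recovery are censored when they occur, 28-day recovery is overstated by about 5-6 points at 10% deaths and 9-12 at 17%, and by 2-3 at 5%. These figures assume 65-75% recovery, constant hazards and no other early censoring. The mortality range comes from general figures in protocol 2.2, and true mortality under the entry criteria is unknown. In the fever row the figures apply only to the share of patients who die with fever ongoing, which the documents do not allow one to estimate.

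The documents do not support saying that the SAP prescribes the biased version, only that it permits it. The consequence is confined to two endpoints that are exploratory in the current protocol and have no p-values. The change is worth making because the better method is already written in the table, but neither the primary result nor the mortality result depends on it.

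**What to change.** In both rows of Table 8.1:

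1. Give patients who die without the event time = D28 and censor them there, as the response row does. Alternatively, report Aalen-Johansen cumulative incidence with death as a competing event. The two agree at day 28 when there is no other censoring before then; if withdrawals or transfers are more than a few, the second is the safer choice.
2. State the censoring time for every other participant without the event: still on oxygen or febrile at day 28, discharged without the event, withdrawn or transferred.
3. In the fever row, state the time horizon, and say whether a never-febrile patient who dies is meant to count as recovered on day 0.

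The oxygen status from the day-28 telephone call should not be used as an event time for patients discharged on oxygen. The call records need as yes or no, with no stop date, and the endpoint ends at discharge by its own definition.

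The cost is a few sentences in the SAP and the reuse of a derivation already planned for the response endpoint. No new data are needed.

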4.3. Exploratory Endpoints

- Time since randomization until improvement in oxygenation, (defined as independence from supplemental oxygen) during 28-day assessment period (or discharge, whichever comes earlier)**
- Number of days with hypoxia defined as SpO₂ < 93% breathing room air or the dependence on supplemental oxygen after randomization to Day 28 (or discharge, whichever comes earlier)**
- Time since randomization until absence of last fever (defined as 37.1°C or more) for more than 48h without antipyretics**
- **change in CRP levels between day 1 and day 6, and between day 1 and day 15 (or discharge in each case**
- **change in ferritin levels between day 1 and day 6, and between day 1 and day 15 (or discharge in each case).**
- Incidence of SARs/SUSARs during 28 days**
- Duration of hospital stay**
- Duration of hospital stay in survivors**
- **Change from baseline in 6-point ordinal scale to Day 6, Day 15 and D28 (by phonecall) post randomization**

- Percentage of participants reporting at least a 2-point improvement sustained to D28 or discharge
- AUEC/Time using the 6-point score recorded daily – up to D15, D28 and all data recorded
- Percentage of participants who record a 2-point improvement from baseline or discharge at D6, D15 and D28
- Percentage of participants not deteriorating according to the ordinal scale by 1 or 2 points on D6, D15 and D28
- 6-point Ordinal Scale at 6 and 15 days (or discharge whichever comes first) and day 28 (phone call), in relation to serum D-dimers and complement C5a levels at baseline

- Time since randomization until first use of high-flow oxygen devices or non-invasive mechanical ventilation or invasive mechanical ventilation or ECMO in non-ventilated patients (i.e. excluding patients who are ventilated within 24h prior to or after randomization) during 28-day assessment period
- duration of ventilator-free days after randomization to Day 28 (or discharge, whichever comes earlier)
- Duration of invasive mechanical (including ECMO) and non-invasive mechanical ventilation in ventilated patients
- Duration of ICU stay in patients that enrolled in trial on invasive or non-invasive mechanical ventilation for less than 24h prior to or after randomization during 28-day assessment period
- Duration of ICU stay in patients that enrolled in trial that were on invasive or non-invasive mechanical ventilation or high-flow oxygen devices within 24h prior to or after randomization during 28-day assessment period

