should continue prophylactic antibiotics once daily for 14 days after the last dose of Zilucoplan®. If the participant is discharged before D28, daily prophylactic antibiotic treatment will be taken orally until 14 days after last dose of Zilucoplan®. For Arm B, the 28-day assessment period comprises SOC treatment up to 28 days post randomization or hospital discharge, when the D28 nominal day procedures. Arm B will only have 1 week of IV prophylactic antibiotics once daily, starting on D1. If hospital discharge occurs before D28 post-randomisation, both SOC and antibiotic treatment will cease and the D28 nominal day procedures will occur by telephone.

For both arms, whilst in hospital, assessments will continue on a daily basis as possible, until discharge or Day 28 is reached. If discharge is prior to D28, no daily assessments will be carried out – just the D28 telephone call.

The maximum time window for an eligible participant signing the informed consent document (and starting screening) and being randomised is 24 hours. It is assumed that first dose occurs very soon after randomisation.

An interim analysis (Interim 1) of the primary endpoints is planned after approximately half the planned number of participants have been dosed and had the opportunity to complete D15 assessments. The purpose of the interim analysis is to understand if there is already enough evidence to prompt further work on COVID-19 treatment with Zilucoplan®. There is currently no plan to stop the study based on interim results at this stage. Other endpoints may be summarised as the data allows. Safety data will also be reviewed and summarised as appropriate.

There will also be an interim analysis (Interim 2) when all participants have had the opportunity to complete D28 procedures (by phone call) to assess the primary endpoints, response rate, time to response, time to discharge and 28-day mortality, as appropriate. These analyses will enable key results to be understood as soon as possible, without compromising the study. In addition, safety will be summarised by incidence of TEAE and SAE by treatment arm. Graphs showing the time course for oxygen levels and 6-point ordinal score and Kaplan-Meier plots for time-to-event variables will be provided.

Final analyses will be carried out after all participants have either discontinued prematurely from or completed the study, by completing the follow-up visit.

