Secondary Objective	Endpoint	Measurement

1)continued: To study if early intervention with Zilucoplan® affects clinical outcome defined by duration of hospital stay, 6-point ordinal scale, time to defervescence, supplemental oxygen use, SOFA score
	
Number of days with fever (defined as 37.1°C or more) during 28-day assessment period
 
Time since randomization until absence of LAST fever (defined as 37. 1°C or more) for more than 48 h without antipyretics (use last fever to account for possibility that participants have intermittent fever per this definition)
	
Temperature Vital Parameters
 
Antipyretic use in last 24 hours is collected on eCRF on every day. Use highest temperature recorded in last 24 hours, not the 7-10am temperature

	
Duration of hospital stay
	
From DATES eCRF

	
Duration of hospital stay of survivors
	
From DATES

	
Number of days requiring supplemental oxygenation after randomisation to Day 28 (or discharge, whichever comes earlier)
 
Time since randomization until improvement in oxygenation (defined as independence from supplemental oxygen) during 28-day assessment period (or discharge, whichever comes earlier)
	
Number of days where Suppl O₂ = ‘Y’ from Vital parameters
 
Independence from supplementary oxygen means nor further ‘Y’ after a ‘N’

	
Number of days with hypoxia (defined as SpO₂ <93% breathing room air or the dependence on supplemental oxygen after randomisation to Day 28 (or discharge, whichever comes earlier)
	
Use SpO₂ (%) and Supple O₂ (Y/N) from Vital parameters

Secondary Objective	Endpoint	Measurement

2) To study if early intervention with Zilucoplan® affects progression to mechanical ventilation and/or ARDS
 
And
 
Duration of ICU stay
	
Duration of ventilator free days after randomisation to Day 28 (or discharge, whichever comes earlier)
 
Duration of invasive mechanical (including ECMO) and non-invasive mechanical ventilation in ventilated participants
	
Use data from Vital parameters (include all days, where NIV, IV and ECMO='N')
 
Complement of above (exclude participants who are not ventilated i.e. do not include these with a duration of 0)

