8.2 Statistical analysis of the secondary efficacy endpoint(s)

There are several secondary endpoints that cover each of the secondary objectives and a list is provided in the table listing the secondary endpoints in Section 2.2.1.2. Some of these endpoints are different derivations from the same collected data. In addition, some of the endpoints collected for one objective, may be the inputs to derivations for endpoints for the same objective or for another objective.

Data types for the secondary efficacy endpoints fall into the following main categories: continuous (for example, change from baseline (including the various ordinal categorical endpoints), number of days with 'condition'), ordinal categorical, binary ('responder' Y/N), time to event or duration of event.

Table 8.1 describes the analyses of each secondary endpoint listed in Section 2.2.1.2 and identifies which efficacy objective (2-6) the endpoint is addressing. Brief details of any derivations and analysis methods used are provided. Further details are included in the mock TFL shell document. In the event the data for some of these endpoints indicate that analysis through fitting models is not appropriate, for example too few events for a formal analysis on response or mortality rates, or time to event analyses, the analyses will not be carried out and only listings, figures and summaries provided.

Some patients may withdraw from the study or be transferred to another hospital prior to discharge through medical improvement. If data have been collected from another hospital post discharge from the first hospital, these data will be listed. This will be for variables or derived variables which would have included data from these patients. For example, duration of stay in hospital. However, for variables only including data up to a relative day prior to discharge/transfer from the first hospital, these patients will be included in the analysis/summary

for that period but set as missing for the other periods. Residual plots will be reviewed to determine any influence these participants may have had on the results.

Table 8.1

Endpoint	Derivation	Analysis

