
Objective 2 Incidents of participants reporting each severity rating in 6-point ordinal scale at D1, D6, D15 and D28
	
Percentages for each ordinal score on each day are based on N in each treatment arm on D1. An additional category (score=7) to be created to indicate participants who have withdrawn from the study for any reason or transferred to another hospital. Add label for score category=7 as ‘Withdrawn’. Participants who die (score=1) or are discharged from hospital due to medical improvement (score=6) or are withdrawn (score=7) remain in both the numerator and denominator for these categories on subsequent days by using LOCF for discharge, death and withdrawal. Only use LOCF for participants whose final recorded score is 1, 6 or 7. For the interim, all other subjects whose final recorded score during the period up to 28 days is not equal to 1, 6 or 7, impute a score of 8 for their remaining days (up to D28). This is to indicate the percentage of participants who are still on treatment without imputing what their future values may be.
 
Check that ordinal score matches whether participant has been discharged or has died
	
PROC FREQ to create summary table of actual counts and percentages for each of the 6-points on the ordinal scale on each nominal day (D1, D6, D15 and D28) for each treatment
 
Stacked 100% bar chart indicating a snapshot of counts in each category (color coded for scores 1-7 (including 8 in the interim analyses)) on each relative day by treatment arm. A separate graph for each treatment, placed side by side.
 
For final analysis:
 
Logistic regression for data from specified nominal days (D1, D6, D15 and D28). Fixed effect of Score*Treatment indicating whether the pattern across scores is different between treatments on each day.
 
Note: If D1 is pre-dose and therefore baseline, exclude from table and plot.

Endpoint	Derivation	Analysis

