
Objective 2
 
Number of days with hypoxia (defined as SpO₂ <93% breathing room air or the dependence on supplemental oxygen after randomisation to Day 28 (or discharge, whichever comes earlier)
	
Use SpO₂ (%) and Suppl O₂ (Y/N) from Vital parameters to derive indicator variable which flags each day where this condition holds.
 
Derive variable per participant that gives total number of days with condition
	
Summary statistics of variable with Total number of days: n, mean, SD, median, minimum, maximum
 
By treatment arm

Endpoint	Derivation	Analysis

Objective 3 Duration of ventilator free days after randomisation to Day 28 (or discharge, whichever comes earlier)
	
Use data from Vital parameters (include all days, where NIV, IV and ECMO='N')
	
Summary statistics of variable with Total number of days: n, mean, SD, median, minimum, maximum By treatment arm

Objective 3 Duration of invasive mechanical (including ECMO) and non-invasive mechanical ventilation in ventilated participants
	
Complement of above (exclude participants who are not ventilated i.e. do not include these with a duration of 0)
	
Summary statistics of variable with Total number of days: n, mean, SD, median, minimum, maximum By treatment arm

Objective 3 Time since randomization until first use of high-flow oxygen devices or non-invasive mechanical ventilation or invasive mechanical ventilation or ECMO in non-ventilated participants (i.e. excluding participants who are ventilated within 24h prior to or after randomization) during 28-day assessment period
	
Use Vital Parameter CRF and the method of supplementary oxygen variable. Use the date from this CRF to identify when first use occurred. Indicator variable to identify sub-group to be included. Censor if never used any of these ventilation methods at Day 28
	
Kaplan-Meier analysis using PROC LIFETEST. Strata ACTARM. Request Survival plot adjusting axis and heading titles to reflect progression and not response Output statistics: Appropriate statistics from analysis as indicated in mock shell

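### Ventilator-free days are counted only to discharge and give death no value, so the arm comparison reverses when the better arm saves more hospital days than ventilated days

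*SAP*

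**What the plan says.** The endpoint in SAP Table 8.1 (Objective 3) is "Duration of ventilator free days after randomisation to Day 28 (or discharge, whichever comes earlier". The derivation, also given in the SAP 2.2.1.2 endpoint table, is "Use data from Vital parameters (include all days, where NIV, IV and ECMO='N". Protocol 4.3 uses the same window: "duration of ventilator-free days after randomization to Day 28 (or discharge, whichever comes earlier". The planned output is n, mean, SD, median, minimum and maximum by arm.

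Daily records end at discharge: "If discharge is prior to D28, no daily assessments will be carried out – just the D28 telephone call" (SAP section 2). The next row of Table 8.1 derives ventilation duration from the same window: "Complement of above (exclude participants who are not ventilated i.e. do not include these with a duration of 0".

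SAP 4.2 names death and discharge among its forms of missing data and leaves their handling to each endpoint's analysis section. The ventilator-free row gives no handling. Other rows do. In the ordinal-category row, participants who die, go home improved or withdraw "remain in both the numerator and denominator for these categories on subsequent days by using LOCF for discharge, death and withdrawal". The AUEC row says "For discharge, carry forward score=6 for each day post discharge day. For death, carry forward score=1 for each day post death day".

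**The concern.** A ventilator-free count is normally read as more is better. Here the countable days stop at discharge, so a patient who goes home early loses the good days that follow, while one who lingers unventilated in hospital collects them. A patient who dies keeps every unventilated day lived.

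The neighbouring rows for days on supplemental oxygen and days with hypoxia use the same window without this problem at discharge: they count bad days, and a patient discharged off oxygen adds none at home.

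Duration of hospital stay is part of the secondary objective on clinical outcome, so a shorter stay is an effect the trial is looking for. If it occurs, this row could show the better arm as worse. With no test planned, the direction of the means is what a reader would take from it.

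**Working it through.** The documents give no planning figure for ventilator-free days, so there is none to reproduce.

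**Inputs from the documents.** Window and counting rule: SAP Table 8.1 and 2.2.1.2. End of daily records: SAP section 2. Arm sizes 54 and 27: SAP 2.4. Mortality of 40-50% among invasively ventilated patients: protocol 2.2.

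**Step 1: identity.** For a patient with a record on every day, let H be days from randomisation to discharge, death or Day 28, whichever is first, and V the ventilated days among them. The SAP count is F = H - V. If the better arm saves on average h hospital days and v ventilated days per patient, its difference in F is v - h. This is negative when h > v, positive when h < v, and about zero when the stay shortens only through ventilated days.

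**Step 2: single patients.**

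| Patient | SAP count | Fixed 28 days, death = 0 |
|---|---|---|
| Never ventilated, home on D6 | 6 - 0 = 6 | 28 |
| Ventilated 10 days, in hospital to D28 | 28 - 10 = 18 | 18 |
| Dies unventilated on D20 | about 20 - 0 = 20 | 0 |

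**Step 3: closed form on assumed inputs.** Stay and ventilation rates are not in the documents. Assume unventilated patients go home alive after L days. A share p is ventilated: 2 free days, 10 ventilated days, then 45% die and 55% have 4 more free days and go home. The 45% is the midpoint of the protocol's range for invasive ventilation, applied here to NIV as well.

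- Stay = (1-p)L + p(0.55×16 + 0.45×12) = (1-p)L + 14.2p
- SAP count = (1-p)L + p(0.55×6 + 0.45×2) = (1-p)L + 4.2p
- Fixed 28 days, death = 0: 28(1-p) + p×0.55×18 = 28(1-p) + 9.9p

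| Arm | Stay | SAP count | Fixed count |
|---|---|---|---|
| Control: L=12, p=25% | 12.55 | 10.05 | 23.48 |
| Better: L=9, p=15% | 9.78 | 8.28 (-1.77) | 25.29 (+1.81) |
| Better: L=12, p=10% | 12.22 | 11.22 (+1.17) | 26.19 (+2.71) |

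Over L = 8-10 and p = 10-20%, the SAP difference runs from -0.63 to -2.81 and the fixed-count difference from +0.91 to +2.71. Without zeroing deaths (add 0.9p) the fixed-count difference is +0.86 to +2.58, so its sign does not rest on the death convention. Ventilated days saved are 10×(0.25 - p). The SAP sign therefore flips once mean stay is shorter by more than 0.5 day (p=20%), 1.0 day (15%) or 1.5 days (10%).

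**Step 4: simulation.** 20,000 trials of 54 v 27; control L=12, p=25%; log-normal unventilated stay and ventilation time with CV 50%; 2% deaths if unventilated. Share of trials in which the better arm has the lower mean:

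| Better arm | SAP rule | Fixed 28 days, death = 0 |
|---|---|---|
| L=10, p=10% | 66% | 10% |
| L=10, p=20% | 80% | 35% |
| L=9, p=15% | 91% | 21% |
| L=8, p=20% | 99% | 35% |
| L=12, p=20% | 38% | 35% |
| L=12, p=15% | 29% | 21% |
| L=12, p=10% | 20% | 10% |

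The lowest fixed-count figure, just over 9%, is at L=8, p=10%. In the last three rows treatment acts only on ventilation.

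**The case against.** **Low stakes.** The row is exploratory in protocol version 6, is only summarised, and carries no p-value (SAP 3.1). No decision rule uses it. The truncation is visible in the endpoint's name. Ventilated days, length of stay, the daily ordinal chart, AUEC, time to ventilatory support and 28-day mortality are all reported separately. This stands, and it limits the severity. It does not make the row's direction reliable.

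**The remedy may already exist.** SAP 3.2.1.3 allows discharge carry-forward to be extended to secondary parameters, and SAP 8.2 leaves further detail to table shells that were not available. The extension is optional and maps results to nominal days; it does not credit daily counts. The shells would have to contradict the stated window. That no rule for death exists can be confirmed only for the SAP text.

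**The scenarios drive the percentages.** This stands. The 66-99% range applies only where unventilated stay is cut by 2-4 days. The trial's stated rationale is preventing progression to ARDS; if treatment acts only on ventilation, the SAP mean keeps the right sign.

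**Stronger readings.** A reader might infer that the count falls whenever treatment shortens stay. It does not: in the closed form, L=12 with p=10% shortens stay from 12.55 to 12.22 days while the count rises from 10.05 to 11.22. A reader might also take the complement rule for ventilation duration as an error. It is consistent while the window ends at discharge.

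**Conclusion.** The point holds as a conditional one. The stated rule makes the count equal to post-randomisation hospital days, capped at Day 28, minus ventilated days. It can rank a death or a long stay above an early unventilated discharge, and the arm difference reverses when more hospital days than ventilated days are saved.

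The identity needs complete daily records, which the SAP seeks but does not promise. Where ventilation and deaths are equal, an extra hospital day adds one ventilator-free day only if it falls before Day 28. The size in days and the simulated percentages rest on assumed stay, ventilation and mortality inputs; they illustrate the mechanism and do not predict this trial's result.

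The documents do not support a wider conclusion about the trial's efficacy findings: the primary analysis does not use this count. The change is still worth making, because the defect is definite and cheap to remove.

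**What to change.** In SAP Table 8.1, SAP 2.2.1.2 and the matching table shells, and in protocol 4.3 at its next amendment:

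- Define ventilator-free days as days alive and off NIV, invasive ventilation and ECMO over a fixed 28 days from randomisation.
- Score death by Day 28 as 0, including death after discharge.
- Count days after discharge for clinical improvement as ventilator-free, stated as an assumption. List discharged patients whose Day 28 ordinal score is 1 to 5 (dead or back in hospital).
- For patients who withdraw or move to a hospital outside the study before Day 28, set the whole value to missing whatever their later vital status, and show their number and known deaths by arm. SAP 3.6.2 collects SAEs but not ventilation after such a move, so otherwise these patients would have a value only if they died. The SAP 8.2 provision that includes transferred patients "for that period but set as missing for the other periods" does not say whether a partly observed 28-day count is summed or dropped.
- Derive ventilation duration directly from days with NIV, IV or ECMO = 'Y'. The complement would be wrong once home days and a zero for death enter the count.

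No new data are needed. The cost is that death = 0 is a convention that makes the count a composite, and the count is noisier: on the assumed inputs the SD of the arm difference is about 2.1-2.2 days, against 1.3 by the SAP rule. Home days stay an assumption, because the Day 28 call (protocol 9.2) asks about the ordinal scale and oxygen need but not ventilation since discharge. The result should be read beside 28-day mortality and ventilated days.
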